The primary endpoints include HRV, pulmonary function, and biomarkers that include neutrophils, platelets, fibrinogen, C-reactive protein, lactate and plasminogen activator inhibitor. We will also assess endothelial cell function by brachial artery ultrasound. We will carefully monitor the symptoms that subjects may develop during the exposure and over a 24 hour period following exposure. The symptoms include chest pain, dyspnea, pallor, ataxia, and significant heart rhythm anomalies like rapid heartbeat or skipped beats, or arrhythmias noted on EKG. In addition, analyses of blood samples taken after exposure will be scrutinized for abnormalities, including neutrophil counts. Symptoms and/or changes detected in the genotyping blood samples that are considered clinically significant could prompt the study physicians to stop the study. To the extent possible, subjects who fall ill during their participation in the study will be rescheduled.

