#### **OUTCOMES:**

**Pulmonary Function** will be measured before and after exposure. Subjects who have recent abdominal and/or eye surgery or any type of hernia will not be tested for pulmonary function. Subjects will perform spirometry and single breath diffusing capacity (DLCO) on a Sensor Medic Vmax pulmonary function system according to the standard procedure published by the American Thoracic Society. In addition, regional DLCO and pulmonary capillary blood flow (Qc) will be obtained by the intrabreath technique using the same system.

**Heart Rate Variability (HRV)** data will be gathered for 24 hours using a Holter monitor. Specific 10 minute epochs to be analyzed for frequency domain variables include times immediately prior to exposure, immediately following exposure, and approximately 24 hours after exposure. Both time and frequency domain variables will be analyzed, as will abnormal responses (e.g. premature atrial complex, premature ventricular contractions, bradycardia, and tachycardia).

**Flow-Mediated Dilatation (brachial artery ultrasound).** Changes in diameter of arteries caused by reactive hyperemia (endothelium-dependent vasodilatation) and by administration of sublingual nitroglycerin, typically 0.4 mg, (endothelium-independent vasodilatation) will be expressed as a percent change in diameter relative to resting baseline values.

**Peripheral Venous Blood Sample.** Approximately 50 ml of venous blood will be drawn before, immediately after (within 1 hr after exposure ends), and approximately 18 hrs after exposure (Please refer to Table 1 in this section). The site will be prepared with isopropyl alcohol and a tourniquet is applied. Blood is drawn from an antecubital or other appropriate vein. Endpoint measurements will include, but are not limited to the following: blood lipid omega-3 fatty acid levels, biomarkers for specific and non-specific immune responses, coagulation factors, vasoactive factors, and soluble components of PM (e.g. transition metals).

Genotype Screen	Air Exposure	Ozone-Exposure	Follow-up	TOTAL
20	46.2/46.2	46.2/46.2	46.2	251 ml

Table 1. Blood Draws

Our primary endpoints will be HRV measurement, pulmonary function and peripheral venous blood markers. Our secondary endpoints will be arterial wall function and pulmonary function measurements.

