- **Confidentiality** Risk of breach of confidentiality is minimal. All subjects will be assigned a study number which will be used for data recording – not the subject’s name. The study number is all that will be entered into computer databases. All paper files that may contain the subject’s name or screening number are secure in the EPA building that has limited access 24 hours/day. Any abnormal medical findings (CBC, ECG, brachial artery ultrasound image, spirometry) will be discussed with the volunteer and the volunteer will be counseled to seek treatment from his/her personal physician if indicated. Samples will be stored at the U.S. EPA HSF. A numeric coding system will be used to ensure that subjects cannot be directly identified from the samples alone.

**A.4.8. Data analysis.** Tell how the qualitative and/or quantitative data will be analyzed. Explain how the sample size is sufficient to achieve the study aims. This might include a formal power calculation or explanation of why a small sample is sufficient (e.g., qualitative research, pilot studies).

To test our hypothesis that CAP causes adverse cardiovascular effects in GSTM1 null older human volunteers, we will measure a number of relevant endpoints, including blood pressure, HRV, brachial arterial blood flow rate, change in blood coagulation factors, platelets, fibrinogen, c-reactive protein, lactate, plasminogen activator inhibitor, ferritin, and  $\alpha$ 1-antitrypsin. In this study, our primary endpoints will be HRV measurement and peripheral venous blood markers. Our secondary endpoints will be endothelial cell function and pulmonary function measurements. Statistical data analyses will consist of ANOVA for continuous variables and rank sum tests for non-continuous variables pre- and post-exposure. A  $p$  value of 0.05 or less will be considered significant.

The sample size was calculated to detect a difference of 10% change in HRV assuming a standard deviation of 9%. Using GraphPad software, an N of 15 was derived using a power of 0.8 and an  $\alpha$  of 0.05. This study will enroll approximately 30 subjects in order to provide sufficient power to all for the examination of differences between GSTM1 null and positive subjects.

The study cohort will be monitored through genetic screening to ensure that individuals with GSTM1 null genotype are represented in a proportion approximately equal to the prevalence in the US population, about 40%.

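### The protocol ranks its endpoints in three conflicting ways, and several open-ended primary measures share a flat 0.05 threshold, so a positive study is undefined and the false-positive risk is substantially inflated

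*Protocol*

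**What the plan says.** The protocol ranks its endpoints three times.

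- **A.4.5, design description:** "The primary endpoints include HRV, pulmonary function, and biomarkers that include neutrophils, platelets, fibrinogen, C-reactive protein, lactate and plasminogen activator inhibitor". Pulmonary function is primary.
- **A.4.5, OUTCOMES, after Table 1, in two consecutive sentences:** "Our primary endpoints will be HRV measurement, pulmonary function and peripheral venous blood markers. Our secondary endpoints will be arterial wall function and pulmonary function". Here it has both roles.
- **A.4.8, Data analysis:** "our primary endpoints will be HRV measurement and peripheral venous blood markers. Our secondary endpoints will be endothelial cell function and pulmonary function measurements". Pulmonary function is secondary only.

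The contents of the primary set are not fixed either. For HRV, OUTCOMES says "Both time and frequency domain variables will be analyzed" and names no index. The design description names six blood markers. The list of relevant endpoints in A.4.8 leaves out neutrophils and adds coagulation factors, ferritin and α1-antitrypsin. The venous-blood paragraph of OUTCOMES leaves its list open.

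The late HRV reading also differs. The A.4.5 paragraph on the visit after PM exposure takes a 10-minute resting HRV at 18 hours, whereas OUTCOMES puts the last frequency-domain epoch at about 24 hours.

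The decision rule in A.4.8 is that a p "value of 0.05 or less will be considered significant". The sample size there rests on a 10% change in HRV with a standard deviation of 9%, power 0.8 and alpha 0.05, giving an N of 15. About 30 subjects are to be studied so that genotypes can be compared.

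**The concern.** All three rankings are current text, and no reading satisfies all of them. A later analysis plan could not agree with every one, so whoever writes it must choose. If that choice comes after data have been seen, the role of pulmonary function can follow the results.

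The second problem compounds the first. The primary set is a family of measures, the threshold is the same 0.05 for each, and no measure, time point or contrast is given precedence. The protocol does not say whether one significant marker, significant HRV, or some combination would count as a positive study. Under the most natural reading, any one of them would do, and the chance of a false primary finding is then well above the stated 5%. A.4.6 says the data are meant to help set air quality standards, so it matters which result the study is committed to.

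**Working it through.** **1. The plan's own N.** Inputs from A.4.8: difference 10, SD 9, power 0.8, alpha 0.05. Two-sided testing is assumed, since the protocol does not state sidedness.

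- Two-sample t-test, standardised effect 10/9 = 1.11: 13.7, so 14 per group.
- Paired t-test, 9 taken as the SD of one measurement with no correlation between conditions, so SD of the difference 9 × √2 = 12.7: 14.75, so 15.
- Paired t-test, 9 taken as the SD of the difference: 8.5, so 9.

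The stated 15 is reproduced exactly by the second reading and nearly by the first. It is a calculation for one HRV comparison, and it is not in error on this point.

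**2. Counting the primary tests.** The protocol gives no count. The design description in A.4.5 gives HRV (1) + pulmonary function (1) + named blood markers (6) = 8, with HRV and pulmonary function counted once each although both cover several variables. If each were tested separately at two post-exposure times, the count would be 16. Both counts are assumptions.

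**3. Chance of at least one p ≤ 0.05 with no true effect.** For k independent tests this is 1 − 0.95^k. For correlated tests it comes from simulating equally correlated normal statistics (200,000 draws).

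| Tests | Independent | Correlation 0.3 | Correlation 0.5 | Correlation 0.8 |
|---|---|---|---|---|
| 8 | 1 − 0.95^8 = 34% | 30% | 25% | 16% |
| 16 | 1 − 0.95^16 = 56% | 47–48% | 37% | 21% |

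Among independent tests the figure first passes 50% at k = 14 (1 − 0.95^14 = 51%).

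**4. Power if the lead test is the genotype-by-exposure contrast.** A.4.3 targets about 40% GSTM1 null: 0.40 × 30 = 12 null and 18 sufficient. Two-sample t-test on each subject's CAP-minus-air effect, difference 10, two-sided 0.05:

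- 9% is the SD of the within-subject change: power about 0.82.
- 9% is the SD of a single measurement, uncorrelated between conditions (SD of the change 12.7): power about 0.53.

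**5. Cost of keeping eight equal primaries.** Bonferroni gives 0.05/8 = 0.00625 each. Under the favourable reading of the 9%, power for the 12 versus 18 contrast falls from about 0.82 to 0.52.

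**The case against.** **Multiplicity belongs in the analysis plan.** A method for multiple testing is commonly left to a statistical analysis plan, which is not shown here, and a nominal 0.05 level does not say that no adjustment will be made. This stands: the absence of Holm or a fixed order is not itself an error. But the protocol does state conflicting rankings and an open primary set beside a flat threshold, and an analysis plan can resolve those only by departing from some of the protocol's text.

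**The counts are not document facts.** This also stands. A.4.8 speaks of ANOVA pre- and post-exposure, which could mean one repeated-measures test per measure. The dedicated 18-hour visit follows the particle exposure only, so doubling 8 to 16 is not straightforward. The percentages are illustrations.

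**A positive result is likely to be a chance finding.** A reader might infer this, but the documents do not support it. On eight tests the risk is 34% at most. It exceeds one half only with about 14 or more roughly independent tests, and even 16 tests stay below one half at the correlations examined.

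**A.4.8 could be taken as governing.** It is the data-analysis section, and its cardiovascular hypothesis fits secondary status for pulmonary function. That is a reasonable guess at the intention, but nothing in the protocol gives A.4.8 precedence, and it leaves the HRV variable and the marker set open.

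**Blood markers are primary in all three statements.** True. The protocol is consistent on that, so demoting them is an option for the sponsor and not something that the contradiction requires.

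**Conclusion.** The concern holds. The role of pulmonary function is contradicted within and between sections, the blood-marker lists do not match, the late HRV reading is given two times, and no lead measure is named under a flat 0.05 rule. What counts as a positive study is therefore undefined.

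The false-positive risk is substantially inflated if any one primary result suffices: about 34% for eight independent tests and 16% to 30% with correlation 0.8 to 0.3, or roughly three to seven times the nominal 5%. For sixteen tests it is about 56%, or 21% to 48% with the same correlations. These figures rest on the assumed counts, equal correlations and no adjustment.

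A reader might also infer that the lead HRV index can be recovered from the 10% and 9% in A.4.8. It cannot, because no index is named there, and the meaning of the 9% is open as well.

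**What to change.** 1. Put one identical endpoint list in the A.4.5 design description, in OUTCOMES and in A.4.8, with pulmonary function in one role and a closed list of blood markers.
2. Reconcile the 18-hour and 24-hour statements of the late HRV reading.
3. Have the sponsor name the single HRV variable, time point and contrast to which the 10%/9% calculation applies, and make that the lead primary test at two-sided 0.05.
4. Keep the blood markers as further primary or key secondary measures under a fixed order or Holm, or label them exploratory.
5. If the lead contrast is genotype by exposure, say what the 9% SD refers to and restate the power for about 12 null and 18 sufficient subjects.

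Items 1, 2 and 4 need wording only. The costs are that a nominal p of 0.05 or less on one blood marker could no longer be called a primary finding by itself, and that the restated power may be less favourable: about 0.53 instead of 0.82 if the 9% describes a single uncorrelated measurement.

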Numerous epidemiological studies have demonstrated an association between acute and chronic exposure to ambient levels of particulate matter (PM) and various adverse cardiopulmonary effects including mortality, respiratory tract infection, exacerbation of asthma, chronic bronchitis, ischemic heart disease, and stroke (see review, (1)). A recent national scale epidemiological study has shown that short-term exposure to particulate matter (PM) is associated with increased rates of hospital admission for cardiovascular and respiratory symptoms. The cardiovascular risk tended to be higher in the Eastern United States. This study also indicated a disproportionate risk among the elderly who are exposed to PM (2). Dietary factors such as intake of omega-3 fatty acids have been linked to human susceptibility to the adverse effects of ambient PM (14). Although air pollution exposure has long been known to be a risk factor for respiratory disease, over the last decade, a growing body of epidemiological studies has heightened concern over elevated rates of cardiovascular events related to both short-term and long-term exposure to PM (3). The risk of death from cardiovascular disease (myocardial infarction, heart failure, and fatal arrhythmias) in response to chronically high levels of air pollution was much greater than that from lung disease (4-6). Short-term elevations in ambient PM levels are capable of evoking cardiac arrhythmias, worsening heart failure, and triggering acute atherosclerotic/ischemic cardiovascular complications, particularly in certain at-risk subsets of population (3). PM exposure can result in increases in heart rate, and decreases in heart rate variability (HRV; defined as changes in mean heart rate during 24 hrs, which is a reflection of autonomic tone on the heart (7)). PM has been associated with transient increases in plasma viscosity (8), endothelial dysfunction (9) and acute-phase reactants (10, 11) such as C-reactive protein (12). Animal

studies have suggested that long-term exposure to low concentration of PM altered vasomotor tone, induces vascular inflammation and potentiates atherosclerosis (13). Despite a decade of intensive studies, much about the PM health effects problem, especially the cardiovascular effect, is still not well understood. The present study is designed to test the hypothesis that genetic expression of the Phase II metabolizing enzyme GSTM1 alters the outcome of adverse responses to PM exposure.

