## **Exposure Day**

In order to participate in this study, subjects will be required to:

- Avoid smoke and fumes for 24 hours before all visits.
- Avoid drinking alcohol 24 hours before all visits.
- Avoid strenuous exercise for 24 hours prior to and after all visits.
- Refrain from eating pan fried and/or grilled foods after midnight prior to the exposure day.
- Refrain from ingesting caffeine for 12 hours prior to all study visits.
- Eat a light breakfast on the exposure day.
- Bring a lunch to each exposure day. The lunch composition will be specified to minimize potential variations that could affect the arterial diameter measurements. Subjects will be compensated for the cost of the lunch.

**Pre-exposure:** On the day of the study, the subject will report to the medical station in the HSF at which time the general health of the subject will be evaluated and the appropriate pre-exposure measurements (blood pressure, HRV, endothelial cell function by brachial artery ultrasound (BAU), pulmonary function by spirometry and diffusion limited uptake of CO (DLCO), and blood sampling) will be completed.

- **HRV measurement** will be done with the use of a Holter monitor. Electrodes for HRV measurement will be placed. The skin in the areas of electrode placement will be cleaned and shaved (if necessary) to ensure that the electrodes will remain securely attached. These leads will be connected to a Holter monitor and will remain in place for approximately 48 hours. Standard telemetry leads will also be placed, and removed when the patient leaves for the day. The subject will then be allowed to relax for 20-30 minutes in a reclined position.

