The concentration of particles delivered to the chamber will vary depending on the levels of naturally occurring particles in the Chapel Hill air. Although 24 hr averages seldom exceed 15-20 ug/m^3, peak values in the summer can be as high as 50-60 ug/m^3 with lower values during the rest of the year. A face mask is used to reduce the daily and seasonal variability of PM concentration. Our past experience provides a basis to expect the particle mass delivered to the mask will be up to 600 ug/m^3. The particle burden, on a mass basis presented to the volunteer will not exceed an exposure an individual receives over a 24 hour period while visiting a typical urban center in America on a smoggy day. The particle mass of the outdoor air entering and exiting the aerosol concentrator will be monitored continuously. Filter samples will be obtained from the devices located upstream from the chamber and analyzed for both mass and chemical composition of particles. If it is confirmed that particulate mass levels exceed 600 ug/m^3 for greater than 6 minutes, exposure will be terminated. The process for confirmation may take up to

additional 10 minutes. The shutdown procedure involves venting a valve on the exposure chamber, which markedly reduces the particle exposure, and alerting the investigator with both auditory and visual signals leading to removal of the subject from the chamber. Blood pressure, telemetry, and oxygen saturation will be measured during the exposure period.

**Immediate Post-exposure:** Subjects will be released while wearing the Holter and blood pressure monitors. Symptoms questionnaire after exposure will be collected. Blood pressure, lung function, endothelial cell function, and heart rate variability will be measured and approximately 46.2 ml of blood samples will be collected.

**Eighteen Hours Post-PM exposure:** Eighteen hours after the exposure, the subjects will return to the HSF to undergo a brief medical evaluation, including blood pressure, spirometry (pulmonary function testing) and endothelial cell function (BAU) measurements. The subject will then be allowed to relax for 20-30 minutes in a reclined position, after which a 10-minute resting HRV measurement will be obtained, and approximately 46.2 ml of blood will be taken. Holter monitor will be removed.

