**General measures to minimize the risks:** Medical screening of the potential subjects is designed to exclude those that may be at risk from the study procedures. A qualified physician is available in the building whenever a subject is undergoing any procedure. The exposure will be terminated for any rapid change in symptoms, tachycardia and/or arrhythmia, decline in arterial oxygen saturation, or for any distress of concern to the volunteer or the console operator. Medical staff and medication are immediately available (within the building) should it be necessary. HSF has a fully stocked medical station and the University of North Carolina Hospital is a short distance from the HSF. On days after exposure subjects will be urged to contact the medical station should they experience any of the following symptoms: epistaxis, persistent cough, chest pain, dyspnea, wheezing, hoarseness, or sore throat. Risks associated with specific study procedures are as follows:

- **Pulmonary function tests** (spirometry) are standard non-invasive techniques that are commonly used in studies of pulmonary function on populations of all ages and entail little or no risk to the subject. The intrabreath technique uses a single breath of 0.3 % acetylene uptake for measurement of pulmonary blood flow (cardiac output). Although large doses of acetylene can cause nausea, vomiting, and headache our subjects will be exposed to a single inhalation of a low

concentration of acetylene for a brief period of time. Thus the risks of these complications to our subjects are extremely low.

- **ECG and heart rate variability** are standard non-invasive techniques commonly used for heart rate and rhythm analysis and entail little or no risk to the subject. There is the possibility that preparation of the skin for electrode placement and removal may cause skin irritation, itching, or soreness in some subjects.

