- **CAP Exposure .** The subjects in this study will be exposed to an inhaled particle mass that does not exceed what they would encounter over 24 hours in a typical urban environment on a smoggy day. It is expected that particulate exposure levels will be up to 600 ug/m^3 and the exposure will be terminated if the level exceeds 600 ug/m^3 for greater than 6 minutes. Thus while we cannot completely rule out the possibility of an adverse effect, since we are exposing the volunteers to a particulate exposure burden they would likely encounter if visiting a large city, we feel the risk posed to volunteers is very small. Possible health effects of acute exposures to air pollution particles include chest pain, mild dyspnea, headache, cough, and, wheeze. All of these effects would be expected to resolve spontaneously within hours of exposure cessation. The particulate exposure may possibly cause increased airways inflammation. It is also possible that exposure could uncover a previously unidentified pre-existing cardiac condition that could present a health risk to a subject. During the exposures, subjects will be continuously monitored during the entire exposure by direct observation. A physician on duty in the facility will be available when exposures are occurring. Heart rate, continuous electrocardiogram via telemetry, and SaO2 by pulse oximetry will also be monitored continuously, and blood pressure will be monitored every 15 minutes. Indications for terminating the exposure include significant respiratory distress or dyspnea, chest or angina-like pain, significant cardiac arrhythmias, pallor, or ataxia. Subjects will be aware that they can terminate their exposure for any reason and still

Field Cod

receive compensation for the entire session. The investigators or duty physician will end the exposure if the subject is found to be suffering from any adverse effect. Full resuscitation equipment will be available at all times during exposures and in the event of an emergency, after initial medical assessment, patients will be transported to UNC Hospitals Emergency Department for continued treatment.

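### The list of symptoms that should make a subject call after exposure omits rapid or skipped heartbeats, which the plan says it will monitor for 24 hours

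*Protocol*

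**What the plan says.** Four parts of the protocol bear on this.

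- **Call-back instruction (A.4.7, general measures to minimize the risks).** It is worded for the days following an exposure and asks the subject to get in touch with medical staff. Its trigger list reads: "should they experience any of the following symptoms: epistaxis, persistent cough, chest pain, dyspnea, wheezing, hoarseness, or sore throat".
- **In-chamber stopping (same paragraph of A.4.7).** "The exposure will be terminated for any rapid change in symptoms, tachycardia and/or arrhythmia, decline in arterial oxygen saturation". The list continues with any distress that worries the volunteer or the console operator. The CAP Exposure item of A.4.7 repeats significant arrhythmia as a reason to stop.
- **Symptom monitoring (A.4.5).** "We will carefully monitor the symptoms that subjects may develop during the exposure and over a 24 hour period following exposure". The symptoms named there include "significant heart rhythm anomalies like rapid heartbeat or skipped beats, or arrhythmias noted on EKG".
- **Monitoring after release (A.4.5).** On telemetry: "Standard telemetry leads will also be placed, and removed when the patient leaves for the day". On going home: "Subjects will be released while wearing the Holter and blood pressure monitors". The HRV item of the pre-exposure section keeps the Holter leads on for about 48 hours. The subject returns 18 hours after the CAP exposure for a brief medical evaluation, and the Holter is then removed.

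**The concern.** The protocol treats rhythm disturbance as a hazard of this exposure. The rationale in A.4.2 says: "Short-term elevations in ambient PM levels are capable of evoking cardiac arrhythmias". The CAP Exposure item of A.4.7 adds: "It is also possible that exposure could uncover a previously unidentified pre-existing cardiac condition that could present a health risk to a subject". It also stops an exposure for arrhythmia and commits to 24 hours of symptom monitoring that names rapid and skipped heartbeats.

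The one instruction written for a subject at home leaves rhythm out. The list includes hoarseness and sore throat, and it has no catch-all for other worrying symptoms, although the in-chamber rule has one. A 50-75-year-old who feels palpitations after going home from the CAP exposure, without chest pain or dyspnea, is not asked to call. What is at stake is how soon medical staff learn of such an event. No estimate or test depends on it.

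**Working it through.** The protocol gives no figure to reproduce here. The check compares the lists and adds a short clock calculation.

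**1. The call-back list.** It has 7 entries: chest pain, dyspnea, wheezing and persistent cough (chest symptoms), and epistaxis, hoarseness and sore throat (nose and throat). Rhythm symptoms: 0 of 7.

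**2. Against the A.4.5 monitoring list.** Leaving aside arrhythmias seen on EKG, A.4.5 names 6 items. On the call-back list: chest pain and dyspnea = 2. Not on it: pallor, ataxia, rapid heartbeat and skipped beats = 6 - 2 = 4. The point is confined to the two rhythm items, because A.4.2 names arrhythmia as something short-term particle elevations can provoke. It says nothing comparable about pallor or ataxia.

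**3. What would reveal a rhythm event after release.**
- Telemetry: ends when the subject leaves.
- Holter: continues, but the protocol describes no transmission, alarm or review while the subject is at home.
- Ambulatory blood pressure monitor: worn until bedtime, with no live review described.
- 18-hour visit: a medical evaluation, but only then.
- The subject's own call: the only earlier route described, and the list does not request it for rhythm symptoms alone.

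**4. How long the interval is.** Inputs: check-in 2 h 15 min before exposure starts (Operations Plan, Appendix A), an exposure day of about 8 h (B.3), a 2 h exposure, and the visit at 18 h.
- Release, from start of exposure: -2.25 + 8 = 5.75 h.
- Release, from end of exposure: 5.75 - 2 = 3.75 h.
- To the visit, if 18 h runs from the end of exposure: 18 - 3.75 = 14.25 h.
- To the visit, if 18 h runs from the start: 18 - 5.75 = 12.25 h.
- Section 2.0 of the Operations Plan allows no particle session before 10:00, so release falls at about 10:00 + 5 h 45 min = 15:45 or later. The interval covers the evening and night.

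The 8 h day is approximate. A change of 1 h moves each interval by 1 h.

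**The case against.** The strongest objection is that the deciding text is not available. A.4.7 summarises for the IRB what subjects will be urged to do, whereas what they take home is the signed consent form and any discharge instructions. Those pages are not shown and may mention palpitations. This stands as a limit, and no one can conclude from the documents that subjects were left uninstructed. It does not make the A.4.7 list complete.

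Second, a reader might infer that A.4.5 and A.4.7 contradict each other. They do not. A.4.5 says what the study team monitors; A.4.7 says when a subject should phone. The gap is an omission.

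Third, a reader might infer that rhythm goes unmonitored overnight, or that the risk is large. The documents do not support either. The Holter keeps recording. A.4.4 requires a normal resting ECG and excludes a history of arrhythmia, angina or infarction, pacemakers and known cardiovascular disease. The rationale says the effect applies particularly to certain at-risk subsets. Of the five possible acute effects listed under CAP Exposure, the call-back list covers four: chest pain, dyspnea, cough and wheeze. What remains is isolated palpitations at home.

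Fourth, the instruction refers to days after exposure, which may not include the exposure evening. The 12 to 14 hour interval counts as time under the instruction only if it does. That ambiguity is itself worth removing.

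Finally, a reader might go on to ask for light-headedness to be added, or for the symptom questionnaire's printed 4-hour time point to become 18 hours. The first is not argued from anything in the A.4.5 list. The second could remove a check that falls close to release, and the automated OMEGACON questionnaire that will be used unmodified is not shown.

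**Conclusion.** The omission is real and small. The call-back list has no rhythm symptom, although the same protocol names such symptoms for 24-hour monitoring and stops exposures for arrhythmia. On the documents, isolated palpitations at home would come to light only at the 18-hour visit or when the Holter is read, unless the subject calls unprompted.

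This rests on three assumptions: the take-home instructions match A.4.7, the Holter is not reviewed live, and the exposure day lasts about 8 hours. No event rate can be derived, so the size of any harm is not quantified. It is a minor improvement to subject safety and touches no endpoint, analysis or in-chamber stopping rule.

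**What to change.** In the general measures paragraph of A.4.7, add rapid or skipped heartbeats to the symptoms that should prompt a call, and state that the instruction applies from release on the exposure day. Check the consent form and any take-home sheet, and add the same words if they are missing.

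This needs no new visit, procedure or measurement. The cost is a few calls for benign palpitations and, if the subject's written instructions must change, a minor IRB amendment.
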